7.0 COMPLIANCE TO CIP

7.1 STATEMENTS OF COMPLIANCE

The investigator will not start enrolling subjects or requesting informed consent from any subject prior to obtaining IRB/EC approval and Competent Authority approval, if applicable, and authorization from the sponsor in writing for the study.

In case additional requirements are imposed by the IRB/EC or Competent Authority, those requirements will be followed, if appropriate. If any action is taken by an IRB/EC, and regulatory requirements with respect to the study, that information will be forwarded to St. Jude Medical.

7.2 ADHERENCE TO THE CLINICAL INVESTIGATION PLAN

A deviation is defined as an event where the clinical investigator, site personnel, sponsor or sponsor representative did not conduct the clinical study according to the Clinical Investigational Plan (CIP), IRB/EC requirements or the Investigator Agreement. The investigator is not allowed to deviate from the CIP, except as specified under emergency circumstances.

Clinical Investigational Plan

In some cases, failure to comply with the CIP may be considered failure to protect the rights, safety and well-being of subjects, since the non-compliance exposes subjects to unreasonable risks. For example, failure to adhere to the inclusion/exclusion criteria: these criteria are specifically defined by the Sponsor to exclude subjects for whom the device is not beneficial and the use involves unreasonable risks. This may be considered failure to protect the rights, safety and well-being of the enrolled subject. Similarly, failure to perform safety assessments intended to detect adverse events may be considered failure to protect the rights, safety and well-being of the enrolled subject. Investigators should seek minimization of such risks by adhering to the CIP.

Simultaneously, in the event that adhering to the CIP might expose the subject to unreasonable risks, the investigator is also required to protect the rights, safety and well-being of the subject by intentionally deviating from the requirements of the CIP, so that subjects are not exposed to unreasonable risks.

It is the responsibility of the investigator to provide adequate medical care to a subject enrolled in a study.

Regulations require that the PI maintain accurate, complete, and current records, including documents showing the date of and reason for every deviation from the Clinical Investigational Plan. Relevant information for each deviation will be documented on a Deviation Case Report Form (CRF). The site will submit the CRF to St. Jude Medical.

Regulations require investigators obtain approval from St. Jude Medical and the IRB/EC [as required] before initiating changes in or deviations from the protocol, except when necessary to protect the life or physical well-being of a subject in an emergency. Under emergency circumstances, deviations from the CIP to protect the rights, safety and well-being of human subjects may proceed without prior approval of the sponsor and the IRB/EC. Such deviations shall be documented and reported to the sponsor and the IRB/EC as soon as possible, but no later than 5 working days.

Prior approval must be requested when the PI anticipates, contemplates, or makes a conscious decision to depart from the CIP, except when unforeseen circumstances are beyond the investigator's control (e.g. a subject who fails to attend a scheduled follow-up visit, a subject is too ill to perform a CIP-required test, etc.). All deviations, including those beyond the investigator's control, must be reported on a CRF.

To obtain approval, the Principal Investigator may call or email and discuss the potential deviation with St. Jude Medical or designee prior to initiating any changes.

All deviations must be reported to appropriate regulatory authorities in specified timelines (if appropriate).

Investigator will notify St. Jude Medical and the reviewing IRB/EC within 5 working days of:

- Any deviation to protect the life or physical well-being of a subject in an emergency
- Any failure to obtain informed consent

Investigators or the designee must notify St. Jude Medical, Inc. as soon as possible and complete the Deviation CRF.

Clinical Investigational Plan

The investigator is required to adhere to local regulatory requirements for reporting deviations to IRB/EC.

7.3 REPEATED AND SERIOUS NON-COMPLIANCE

In the event of repeated non-compliance or a one-time serious non-compliance, as determined by the Sponsor, a Clinical Research Associate or clinical representative will attempt to secure compliance by one or more of the following actions:

- Visiting the investigator
- Contacting the investigator by telephone
- Contacting the investigator in writing
- Retraining of the investigator

If an investigator is found to be repeatedly non-compliant with the signed agreement, the CIP or any other conditions of the clinical study, the Sponsor will either secure compliance or, at its sole discretion, terminate the investigator's participation in the clinical study.

8.0 ADVERSE EVENT, ADVERSE DEVICE EFFECT, DEVICE DEFICIENCY

8.1 DEFINITIONS

8.1.1 Adverse Event (AE)

Any untoward medical occurrence, unintended disease or injury, or untoward clinical signs (including abnormal laboratory findings) in subjects, users or other persons, whether or not related to the investigational medical device under study.

8.1.2 Serious Adverse Event (SAE)

An adverse event that led to:

- Death
- A serious deterioration in the health of the subject, that either resulted in:
 - A life-threatening illness or injury OR
 - A permanent impairment to a body structure or a body function OR
 - An in-patient or prolonged hospitalization OR
 - A medical or surgical intervention to prevent life-threatening illness or injury or permanent impairment to a body structure or a body OR
 - A malignant tumor
- Fetal distress, fetal death or a congenital abnormality or birth defect

Note: A planned hospitalization for a pre-existing condition, or a procedure required by the CIP is not considered a serious adverse event.

8.1.3 Adverse Device Effect (ADE)

An adverse event related to the use of an investigational medical device.

This definition includes adverse events resulting from insufficient or inadequate instructions for use, deployment, implantation, installation, or operation, or any malfunction of the investigational medical device.

Clinical Investigational Plan

This definition includes any event resulting from the use error or from intentional misuse of the investigational medical device.

For this study, ADEs include events related to any St. Jude Medical pressure sensor guidewires.

8.1.4 Serious Adverse Device Effect (SADE)

Adverse device effect that has resulted in any of the consequences characteristic of a serious adverse event or that might have led to any of these consequences if suitable action had not been taken or intervention had not been made or if circumstances had been less opportune.

8.2 PROCEDURE FOR ASSESSING, RECORDING, AND REPORTING ADVERSE EVENTS, DEVICE DEFICIENCIES/COMPLAINTS, ADVERSE DEVICE EFFECTS, SERIOUS ADVERSE EVENTS, AND SERIOUS ADVERSE DEVICE EFFECTS:

Safety surveillance within this study and the safety reporting both performed by the investigator, starts as soon as the subject is enrolled in this study. The safety surveillance and the safety reporting will continue until the last investigational visit has been performed, the subject is deceased, the subject/investigator concludes his participation into the study or the subject/investigator withdraws the subject from the study, except as otherwise specified in the CIP.

Events considered reportable to sponsor are:

- Major adverse cardiac events (MACE) defined as all cause death, documented non-fatal myocardial infarction, and unplanned hospitalization leading to urgent revascularization
 - Myocardial infarction is defined according to the Universal Classification of Myocardial Infarction¹¹ (Appendix B)
 - Unplanned hospitalization leading to urgent revascularization is defined as unexpected hospitalization due to persisting or increasing complaints of chest pain (with or without ST-T changes) AND a revascularization is performed within the same hospitalization.
- Adverse device effects

All above events will be reported to the Sponsor, as soon as possible, but no later than 72 hours of first learning of the event. These will be reported to the Sponsor on dedicated case report forms or through the EDC system. The Investigator will record all adverse events and device deficiencies on the appropriate case report forms

Additional information may be requested, when required, by the Sponsor in order to support the reporting of AEs to regulatory authorities.

The Sponsor will ensure that all events and device deficiencies are reported to the relevant authorities as per regulations.

Records relating to the subject's subsequent medical course must be maintained and submitted (as applicable) to the Sponsor until the event has subsided or, in case of permanent impairment, until the event stabilizes and the overall clinical outcome has been ascertained. Adverse events will be monitored until they are adequately resolved. The status of the subject's condition should be documented at each visit.

Clinical Investigational Plan

The investigator must notify the IRB/EC, if appropriate, in accordance with national and local laws and regulations, of the AEs reported to the Sponsor.

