3.5.2 Point of Enrollment

A patient becomes a subject (enrolled) once he/she has been fully informed about the study, has agreed to participate, signed & dated the consent, has been determined to meet all inclusion criteria

Clinical Investigational Plan

and none of the exclusion criteria, and at least one physiologic coronary pressure measurement with an SJM PressureWire™ has been recorded. Refer to section 3.6 for the Informed Consent Process.

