3.6 INFORMED CONSENT PROCESS

3.6.1 General process

Prior to enrolling in the clinical study, all subjects will be consented, as required by applicable regulations and the center's IRB/EC. Informed consent must be obtained from each subject prior to any data collection. The consent form must be signed and dated by the subject and by the person obtaining the consent.

Medical circumstances may occur where potential subjects require emergent medical intervention, and thus measurements of their FFR and other metrics (i.e. patients experiencing ACS). As a result, and since this is a routine clinical practice observational study, subjects are allowed to be consented after the procedure, but must be consented prior to any data submission.

The Principal Investigator or his/her authorized designee will conduct the Informed Consent Process. This process will include a verbal discussion with the subject on all aspects of the clinical study that is relevant to the subject's decision to participate in the clinical study.

The subject shall be provided with the informed consent form that is written in a language that is understandable to the subject and has been approved by the center's IRB/EC. Failure to obtain informed consent from a subject prior to study enrollment should be reported to St. Jude Medical within 5 working days and to the reviewing center's IRB/EC consistent with the center's IRB/EC reporting requirements.

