6.3 BASELINE VISIT

The following enrollment activities are performed after the subject has been screened and may occur before or after the study procedure/visit.

- The principal or delegated study personnel determine subject eligibility for the study
- Record enrollment information (name of the study, date of consent and inclusion/exclusion information) in the hospital records and complete and submit the Enrollment form in a timely manner (recommended within 5 days)
- Notification of a consented subject to the sponsor will take place when the sponsor receives the baseline form

If a subject does not meet all inclusion criteria or meets any of the exclusion criteria, the subject cannot participate in the study and cannot be enrolled.

In case the subject was already consented to participate in the study and an FFR was performed, and it was determined that they do not meet inclusion/exclusion criteria, the following actions will be taken:

- Document enrollment information (name of the study, date of consent and inclusion/exclusion) in the hospital records; complete the Baseline and Withdrawal Forms. The form(s) must be authorized / approved by the principal or delegated investigator.
 - Inform the subject about the withdrawal.
 - The EC/IRB and Competent Authority should be notified appropriately, as per local regulations, about any deviations with regards to obtaining the informed consent.

The following information will be collected at the baseline visit:

- Medical history
- Demographics- include subject's Year of Birth and Gender
- Current clinical status

Clinical Investigational Plan

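### Safety surveillance starts at enrollment, which needs a recorded wire measurement and may follow the procedure, so part of the wire exposure precedes adverse device effect reporting

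*Combined protocol and SAP*

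**What the plan says.** Section 8.2 fixes the start of the investigator's safety surveillance and reporting: it "starts as soon as the subject is enrolled in this study". The same section lists two event types under "Events considered reportable to sponsor are": MACE and adverse device effects. Both are due "no later than 72 hours of first learning of the event".

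Section 3.5.2 defines enrollment. Consent, eligibility and a wire measurement are all required, the last in the words "at least one physiologic coronary pressure measurement with an SJM PressureWire™ has been recorded".

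Section 3.6.1 adds that "subjects are allowed to be consented after the procedure, but must be consented prior to any data submission". Section 6.3 says that the enrollment activities "may occur before or after the study procedure/visit".

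Section 8.1.3 sets the scope of device effects: "For this study, ADEs include events related to any St. Jude Medical pressure sensor guidewires". The definition carries no time limit.

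Section 6.4, the schedule in 1.1 and Table 1 require a MACE assessment at the procedure. None of them lists an adverse device effect assessment there.

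**The concern.** The device is a guidewire, and exposure to it is confined to catheterization. A surveillance window for its effects should therefore open no later than the moment the wire goes in. Here it opens at an administrative point that cannot come before the first recorded measurement and may come after the procedure is over.

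Adverse device effects are one of only two event types reportable to the sponsor. If sites follow the start rule literally, the count will be too low, and nothing in the data will show it. If some sites follow it literally and others report procedural events anyway, the count will depend on how each of about 200 centers reads the text. Section 12.1.5 also reports serious adverse events after 500, 1000 and 1500 subjects complete follow-up. Serious device effects missed at source would be missing there too. The point concerns device effects; it does not concern the starting date of 12-month MACE.

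**Working it through.** The plan gives no figure to reproduce on this point. The check is one of ordering, followed by a look at what other sections recover.

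**Step 1: order of events under 8.2, 3.5.2 and 3.6.1**

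| Patient | Sequence | Wire use before surveillance starts |
|---|---|---|
| Consented before the procedure | wire in, first recorded measurement, enrolled, surveillance | Introduction up to the first recorded measurement |
| Consented after the procedure | wire in, measurements, wire out, consent, enrolled, surveillance | All wire use in the index procedure |
| Consented beforehand, complication or failure before any measurement | wire in, event, no measurement | All of it; the patient is never enrolled |

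For the third row, section 3.4 promises accounting only for enrolled subjects.

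**Step 2: does another section move the start back?**

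- 8.2 contains a clause deferring to other parts of the plan, but it sits in the sentence on how long surveillance continues, not the one on when it begins.
- The procedural MACE assessment (6.4, Table 1) captures death, myocardial infarction, and unplanned hospitalization leading to urgent revascularization. A wire-related dissection or perforation with none of these is not MACE.
- Section 8.4 makes the investigator responsible for device deficiencies throughout the trial, without tying this to enrollment, and requires an adverse event form when an adverse event is involved. It covers malfunctions, user errors and labeling. It does not cover an injury from a wire that worked as intended and was used correctly, and it does not say whether it reaches patients who are never enrolled.

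What remains uncovered is a wire-related injury that is neither MACE nor a device deficiency and that arises before enrollment.

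**Step 3: how much exposure is involved?**

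Two quantities are needed, and the documents give neither. Let L be the share of subjects consented after the procedure. Let f be the share of wire-use time that precedes the first recorded measurement in subjects consented beforehand. Among enrolled subjects, the share of index wire-use time before enrollment is L + (1 − L) × f.

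| Assumed f | L = 0 | L = 0.25 | L = 0.5 | L = 1 |
|---|---|---|---|---|
| 0.1 | 10% | 32.5% | 55% | 100% |
| 0.2 | 20% | 40% | 60% | 100% |
| 0.3 | 30% | 47.5% | 65% | 100% |

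For example, at L = 0.25 and f = 0.1: 0.25 + 0.75 × 0.1 = 0.325. The share passes one half when L exceeds (0.5 − f)/(1 − f), which is 44% at f = 0.1, 37.5% at f = 0.2 and 29% at f = 0.3. This is a share of time, not of events; events need not be spread evenly over wire use.

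**Step 4: a related inconsistency in timelines**

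Section 8.1.3 counts an adverse event caused by a malfunction or use error as an adverse device effect, so 8.2 applies and gives 72 hours. Section 8.4 gives 5 days for a device deficiency that involves an adverse event. The same event falls under both.

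**The case against.** The strongest reply is that 8.2 states when a duty begins and does not exclude events by date of onset. The 72-hour clock runs from learning of an event, the definition in 8.1.3 has no time limit, and procedural data on late-consented subjects are plainly entered retrospectively. On that reading, a wire event in a late-consented subject becomes reportable once the subject is enrolled. In addition, the case report forms are under separate cover and may ask about device effects at the procedure.

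This reading is possible, and some sites will probably adopt it. But the plan nowhere states it, and the only explicit rule on timing points the other way. It also does nothing for a patient who is never enrolled. Forms that cannot be seen cannot settle the matter.

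Two further objections stand and limit the point:

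- A reader might infer that most wire exposure lies outside surveillance. The documents do not support this. Any physiologic pressure measurement satisfies 3.5.2, so a resting Pd/Pa could be enough. In subjects consented beforehand, later hyperemic measurements, the pullback, other lesions and later secondary procedures can then fall inside the window. Section 3.6.1 explains late consent by emergent cases such as ACS, and the ACS target is 500 of 2000, or 25%. Late consent is not restricted to ACS, so this is only indicative, but at L = 0.25 every entry in the table above is below one half.
- A reader might also want to turn the gap into a confidence bound on the device-effect rate. Section 12 plans no such rate or bound, and none of the six objectives concerns device safety, so there is no planned figure to correct.

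**Conclusion.** The concern holds in a limited form. As written, the start rule in 8.2, combined with 3.5.2 and 3.6.1, puts wire introduction up to the first recorded measurement outside adverse device effect surveillance in every subject. It does the same for the whole index procedure in late-consented subjects. Consented patients with a complication before any measurement drop out altogether. If the rule is followed, device effects are undercounted.

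The size of the undercount is unknown. It depends on the late-consent share and on when in the procedure wire effects occur, and the plan gives neither. It would be wrong to say that nothing else recovers these events: procedural MACE assessment and device deficiency reporting do recover some. The conclusion rests on the literal reading of 8.2; a site that reports earlier-onset events once the subject is enrolled would narrow the gap.

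**What to change.** - **Section 8.2:** state that surveillance for adverse device effects covers the period from first introduction of the PressureWire, and that in subjects consented after the procedure, events from that point are entered from source records once consent is obtained. This stays within the consent rule in 3.6.1.
- **Schedule in 1.1, Table 1 and section 6.4:** add adverse device effect assessment to the Procedure column and to the list of procedural data.
- **Consented patients with a wire introduced but no measurement:** record any device effect and list these patients separately. The enrollment definition and the analysis population need not change.
- **Sections 8.2 and 8.4:** reconcile the 72-hour and 5-day timelines for a device deficiency that involves an adverse event.

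The cost is a few sentences, one added assessment and a small number of extra forms. The reported device-effect count may rise slightly. The change does not reach patients who never consent; their events remain outside the study data.

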8.3 SUBJECT DEATH

8.3.1 Procedure for recording and reporting subject death

All subject deaths are to be documented on the Death case report form and reported to the Sponsor within 72 hours after becoming aware of the event.

8.4 DEVICE DEFICIENCY (DD)/COMPLAINT

During the trial, the investigator will be responsible for reporting all device deficiencies. A Device Deficiency is defined as an inadequacy of a medical device with respect to its identity, quality, durability, reliability, safety or performance and includes malfunctions, user errors and inadequate labeling.

If the device deficiency involves an adverse event, the principal investigator must complete an adverse event form including information on the device deficiency and report to the sponsor within 5 days after becoming aware of the event.

If the device deficiency/complaint does not involve an adverse event, the investigator must notify St. Jude Medical as soon as possible after becoming aware of the device deficiency/complaint by emailing the information to [contact] or calling [contact]. This information will not be collected on a CRF for the study.

St. Jude Medical will manage all device deficiencies related to the identity, quality, durability, reliability, safety or performance of the study device and the reporting to the appropriate regulatory bodies.

9.0 DATA MANAGEMENT

Overall, the Sponsor will be responsible for the data handling.

The Sponsor and/or its affiliates will be responsible for compiling and submitting all required reports to governmental agencies.

Data will be analyzed by the Sponsor and may be transferred to the Sponsor's locations outside of Europe and/or any other worldwide regulatory authority in support of a market-approval application.

St. Jude Medical respects and protects personally identifiable information collected or maintained for this clinical trial. The privacy of each subject and confidentiality of his/her information will be preserved in reports and when publishing any data. Confidentiality of data will be observed by all parties involved at all times throughout the clinical trial. All data will be secured against unauthorized access.

The Principal Investigator or institution will provide direct access to source data during and after the clinical study for monitoring, audits, IRB/EC review and regulatory authority inspections. As required, the Principal Investigator or institution will obtain permission for direct access to source documents from the subject, hospital administration and national regulatory authorities before starting the clinical study.

Clinical Investigational Plan

